4.1 Study Objectives

We propose to study the effects of early initiation of alirocumab in addition to high intensity statin therapy in patients who have previously been treated with moderate-high intensity statins, who present with a type I (spontaneous) acute non-ST segment elevation MI (NSTEMI). Particular attention will be paid to additional LDL lowering effects, as well as the effects on PCSK9 levels and inflammatory biomarkers.

Biomarkers will be collected at baseline, 3 days, and 14 days after randomization.

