13.1 Sample Size

In the ODYSSEY Long Term trial, the addition of alirocumab 150 mg to maximally tolerated statin therapy resulted in a reduction of LDL cholesterol of approximately 60% at 4 weeks⁵. Similar LDL reductions were seen even when used in statin-intolerant

patients, as demonstrated in the ODYSSEY Alternative trial²⁴. We anticipate that patients will have baseline LDL levels of approximately 124 mg/dL on first presentation², and that a >40% in LDL reduction will be observed after treatment with alirocumab + atorvastatin 80 mg on top of what is seen with placebo + atorvastatin 80 mg at 2 weeks (primary endpoint), with a standard deviation of approximately 25%. These estimates lead to a predicted power >99% ($\alpha=0.01$) with a sample size of 20 patients, and of >95% with a 25% loss to follow up at 14 days. We also expect that patients with an acute myocardial infarction to have increased CRP levels, peaking at 72 hours^{22,23}. A sample size of 20 patients will also provide a power of 65-85% to detect a reduction of 33-50% in CRP or IL-6 plasma levels at 72 hours or 14 days with alirocumab + atorvastatin 80 mg on top of placebo + atorvastatin 80 mg (secondary endpoint).

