13.2 Analysis of the data

Continuous variables will be reported as median and interquartile, because of potential deviation from Gaussian distribution. Discrete variables will be reported as N and %. For the primary endpoint, the comparison in the interval change in LDL cholesterol between alirocumab and placebo will be completed using an ANOVA for repeated measures and assessing the P value for time_x_group allocation. P values <0.05 will be considered significant. Missing data will not be input. For the purpose of safety analysis, all patients receiving the investigational drug will be considered, independent of missing data.

14) REFERENCES

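### Section 13.2 does not say which visits enter the primary repeated-measures test and names no sphericity correction; if all three enter uncorrected, the true error at P<0.05 lies between 5% and about 9%

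*Combined protocol and SAP*

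**What the plan says.** Section 13.2 gives the only primary analysis: the LDL comparison "will be completed using an ANOVA for repeated measures and assessing the P value for time_x_group allocation". The threshold is "P values <0.05 will be considered significant". Continuous variables are summarised by median and interquartile range "because of potential deviation from Gaussian distribution". The section does not mention sphericity, an adjustment of degrees of freedom, a covariance structure, a transformation, or the visits that form the time factor.

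On visits, section 4.1 states: "Biomarkers will be collected at baseline, 3 days, and 14 days after randomization". Section 9 takes the second sample at day 3 or at discharge if that is earlier, and allows 3 days either side of day 14. Section 4.3 defines the primary endpoint as one change, from baseline to day 14. The 72-hour LDL change is a separate secondary endpoint.

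Section 13.1 plans 20 patients on an effect worded as "a >40% in LDL reduction will be observed after treatment with alirocumab + atorvastatin 80 mg on top of what is seen with placebo", "with a standard deviation of approximately 25"%. It gives no between-visit variances or correlations.

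**The concern.** With three visits, the ordinary time-by-group F test has its nominal error rate only if the day 3–0, day 14–0 and day 14–3 differences all have the same variance. Here the visits are 3 and 11 days apart, and the first gap shrinks when discharge comes early. Baseline and day-3 LDL may well be closer to each other than either is to day 14. When the three variances differ, the uncorrected test rejects too often under no drug effect.

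This P value is the sole primary decision rule, so any excess favours a positive result. Leaving the correction unstated also lets the analyst choose between a corrected and an uncorrected P value after seeing both.

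**Working it through.** **Inputs from the documents.** 20 patients randomised 1:1, so 10 per arm (sections 2 and 7); visits at days 0, 3 and 14 (4.1); threshold 0.05 (13.2); SD 25% and mean baseline LDL 124 mg/dL (13.1). I take the day-14 change SD as 0.25 × 124 = 31 mg/dL. The other difference SDs and all correlations are assumptions.

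**The plan's own figures.** The only error rate stated for this test is the 0.05 threshold. It is reproduced when the three difference SDs are equal (first row of the table). Section 13.1 also claims "predicted power >99% ($\alpha=0.01$) with a sample size of 20 patients". For a two-sample comparison with 10 per arm this does not reproduce: Φ(40/(25√(2/10)) − 2.576) = Φ(1.00) = 84.2%, or 74.8% with the t distribution. That is a separate matter. It is noted because power enters the cost of the fix.

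**Formula.** Let s be the sum of the three difference variances and q the sum of their squares. Then ε = s²/(6q − s²). It equals 1 under sphericity and has lower bound 0.5. By the Box approximation, the true error of the uncorrected test is P[F(2ε, 36ε) > 3.259], where 3.259 is the 5% point of F(2, 36).

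Example with SDs 12.5, 31, 31: the variances are 156.25, 961 and 961, so s = 2078.25 and q = 1,871,456. Then ε = 4,319,123/(11,228,737 − 4,319,123) = 0.63, and the error is 7.7%.

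**Results by assumed difference SDs** (no drug effect, Gaussian data, at least 100,000 simulated trials per row):

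| SDs 3–0, 14–0, 14–3 (mg/dL) | ε | Box | Simulated, uncorrected | Simulated, Greenhouse-Geisser |
|---|---|---|---|---|
| 31, 31, 31 | 1.00 | 5.0% | 5.0% | 4.5% |
| 28, 31, 28 | 0.98 | 5.1% | 5.0% | 4.5% |
| 25, 31, 28 | 0.94 | 5.3% | 5.1–5.2% | 4.5% |
| 20, 31, 28 | 0.82 | 6.1% | 5.9–6.0% | 4.7–4.9% |
| 12.5, 31, 31 | 0.63 | 7.7% | 7.4–7.5% | 5.0–5.1% |
| 8, 31, 30 | 0.55 | 8.3% | 8.1–8.3% | 4.9–5.1% |

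The ceiling, at ε = 0.5, is 8.8% with 20 patients and 8.9% with 15.

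**Correlation decaying with days apart.** Assume a 3-day correlation of 0.9. The other two are 0.9^(14/3) = 0.612 and 0.9^(11/3) = 0.680, so the difference variances are in the ratio 0.100 : 0.388 : 0.320 and ε = 0.71. Simulated error is 6.7–6.8%. Over 3-day correlations of 0.7 to 0.95 it is about 6–7%. If every second sample came at day 1, it would be 7.7–8.1%.

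**Skewed data.** Lognormal values with equal correlations and a CV of 30–50% give 4.7–5.1%. Skewness alone therefore adds nothing with equal arms of 10.

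**Two visits only.** With baseline and day 14 there is one difference, ε = 1 by definition, and the interaction F is the square of the t statistic on change. Across all simulated settings, including the skewed ones, a t test on the day-14 change had an error of 4.5–5.2%.

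**What a corrected three-visit test still detects.** Take SDs 20, 31, 28, no day-14 effect, and an assumed effect at day 3 only. The Greenhouse-Geisser test is significant in about 18% of trials for 15 mg/dL and about 50% for 25 mg/dL. The correction repairs the error rate but does not make the test specific to day 14.

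**The case against.** The strongest reply is that the analysis may use two visits. Section 13.2 ties the test to the primary endpoint and to an interval change, section 4.3 defines that endpoint as baseline to day 14, and day-3 LDL is a secondary endpoint. Section 4.1 says when samples are taken, not what enters the model. This stands as a possible reading. The text does not settle it, and a repeated-measures analysis of a variable measured three times is just as natural.

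A reader might go further and infer three things that the documents do not support:

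- **That the plan prescribes an uncorrected test.** It is silent, and an adjustment is not ruled out.
- **That the visits certainly violate sphericity, so that 6–8% is the actual error rate.** No covariance is given, and SDs such as 25, 31, 28 leave the error near 5%. The statin argument is also limited: day 3 follows the switch to atorvastatin 80 mg as well, and section 6.1 admits patients already on that dose.
- **That doubt about Gaussian data invalidates the primary P value.** The skewed-data runs show no inflation from this source, and reporting medians does not contradict the test.

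Materiality is also fairly questioned. Against a planned difference of 40 points with an SD of 25, an excess of 1 to 3 percentage points is unlikely to change the conclusion if the drug works as expected. That limits the weight of the point but does not remove it.

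**Conclusion.** The point holds conditionally. If the three collected visits enter without correction, the true type I error at P<0.05 is between 5% and about 9% with 10 per arm. It is about 6–7% under time-decaying correlation and up to about 8% if day-3 LDL stays close to baseline. At a nominal 1%, the level used only in the power statement of 13.1, the assumed difference SDs from the 20, 31, 28 row downwards give 1.6–3.0%. Where in these ranges the trial would fall depends on covariances that the documents do not give. If only baseline and day 14 enter, there is no inflation. This is an under-specified primary analysis that is cheap to repair, not a demonstrated failure of the trial.

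**What to change.** In section 13.2, state that the primary P value comes from the single group contrast in percentage LDL change from baseline to day 14, for example a two-sample t test on that change. It needs no sphericity and cannot be driven by a day-3-only difference. If a three-visit time-by-group test is kept, name the visits and take its P value with Greenhouse-Geisser degrees of freedom. A permutation test that reassigns arm labels to whole patient profiles under the allocation scheme used would also serve.

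No new data are needed. The price is apparent power, part of which came from excess false positives. In one simulated three-visit case with a day-14 effect of 50 mg/dL (about 0.40 × 124), Greenhouse-Geisser lowers power from about 94% to 91% at 0.05, and from about 83% to 74% at 0.01. The single contrast, with a difference of 40 and SD 25, has 92% power at two-sided 0.05 and 75% at 0.01 with 20 patients. Greenhouse-Geisser is also slightly conservative when sphericity holds (4.5% in the first table row).

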Alirocumab in Patients with Acute Myocardial Infarction

A Randomized Controlled Double-Blinded Study

The VCU Alirocumab Response Trial

STUDY PROTOCOL

Principal Investigator: [name], PhD

Sponsor: Virginia Commonwealth University

Funding provided by: Regeneron Pharmaceuticals, Inc. and
Sanofi U.S.

TABLE OF CONTENTS

- 1) PERSONNEL**
- 2) PROTOCOL SUMMARY**
- 3) BACKGROUND INFORMATION AND SCIENTIFIC RATIONALE**
- 4) OBJECTIVES**
 - 4.1 Study objectives
 - 4.2 Study outcome measures
 - 4.3 Study endpoints
- 5) STUDY DESIGN**
- 6) ENROLLMENT IN THE STUDY**
 - 6.1 Inclusion criteria
 - 6.2 Exclusion criteria
- 7) RANDOMIZATION**
- 8) TREATMENT WITH THE INVESTIGATIONAL DRUG**
- 9) STUDY ASSESSMENT**
- 10) POTENTIAL BENEFITS AND RISKS**
 - 10.1 Alirocumab
 - 10.2 Social and psychological risks
 - 10.3 Testing Risks
 - 10.4 Direct benefits to study participants
- 11) ASSESSMENT OF SAFETY**
 - 11.1 Reporting of Adverse Events
- 12) DISCONTINUATION OF TREATMENT AND WITHDRAWAL**
- 13) STATISTICAL CONSIDERATIONS**
- 14) REFERENCES**

1) PERSONNEL

Name	Role	Institution/ Division
[name], PhD	Principal Investigator	VCU, Cardiology
[name]	Regulatory Coordinator	VCU, Cardiology
[name]	Investigator	VCU, Cardiology
[name] [name]	Investigator	VCU, School of Pharmacy
[name], MS	Investigator	VCU, Cardiology
[name]	Investigator	VCU, School of Pharmacy
[name], MS	Investigator	VCU, Cardiology
[name]	Investigator	VCU, Internal Medicine
[name]	Investigational Pharmacy	VCU, School of Pharmacy

2) PROTOCOL SUMMARY

- Title:** **Alirocumab in Patients with Acute Myocardial Infarction**
- Population:** 20 patients aged ≥ 21 years presenting with an acute spontaneous non-ST elevation myocardial infarction (NSTEMI) who are already taking at least moderate intensity statin therapy at time of hospital admission
- Description:** Phase IV clinical trial of the alirocumab, an inhibitor of the proprotein convertase subtilisin/kexin (PCSK9), or placebo added to high-intensity statin (atorvastatin 80 mg) in LDL cholesterol lowering during NSTEMI.
- Objectives:** To determine the effectiveness of alirocumab in further lowering cholesterol LDL and inflammatory biomarkers when initiated acutely in patients with NSTEMI, in addition to high intensity statin, atorvastatin 80 mg.
- Primary Endpoint:** Placebo-corrected percentage change in calculated LDL cholesterol from baseline to day 14.

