4.3 Study Endpoints

Primary Endpoint:

[figure not shown]
- Placebo-corrected percentage change in calculated LDL cholesterol from baseline to day 14.

Secondary Endpoints:

- Placebo-corrected percentage change in calculated LDL cholesterol from baseline to 72 hours;
- Placebo-corrected percentage change in PCSK9 levels from baseline to 72 hours and 14 days;
- Placebo-corrected percentage change in Lp(a) levels from baseline to 72 hours and 14 days;
- Placebo-corrected percentage change in inflammatory markers (hsCRP, IL-6, IL-10, and TNF- α) from baseline to 72 hours and 14 days;
- Safety and tolerability of alirocumab when initiated in the inpatient setting soon after an NSTEMI.

5) STUDY DESIGN

We designed an active-controlled, double-blinded study of alirocumab versus placebo in addition to high intensity statin, atorvastatin 80 mg, in patients who present with acute type I (spontaneous) NSTEMI and who are already taking a moderate-high intensity statin prior to admission.

The study is composed of two treatment arms exploring:

- a) Alirocumab 150 mg given as a single dose subcutaneously + Atorvastatin 80 mg orally daily;
- b) Matching placebo injection subcutaneously + Atorvastatin 80 mg daily.

6) ENROLLMENT IN THE STUDY

Patients who are admitted to the Pauley Heart Center in the VCU Medical Center will be screened for inclusion and exclusion criteria based on a cursory evaluation of the information available in their medical charts. This approach is supported by a partial waiver of informed consent for authorization to access protected health information to allow identification of the subjects. After identifying the potential subjects, the investigators will approach the subjects in a private manner and review the informed consent form approved by the Institutional Review Board. Any additional information about their medical history that is unclear or incomplete from the medical charts will be clarified by speaking with the patients and obtaining confirmatory outside medical records, with the consent of the patients, if deemed necessary.

Patients agreeing to participate in the study will sign the informed consent form and will be given a copy of the consent form signed by the investigator performing the informed consent process. No study procedures will occur prior to the subject signing the approved informed consent.

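### One unqualified P<0.05 rule also covers eight inflammatory comparisons, giving up to about a one-in-three chance of a false significant result on a stated objective; label the secondary endpoints exploratory

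*Combined protocol and SAP*

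**What the plan says.** Section 13.2 describes one inferential analysis, for the primary endpoint (LDL cholesterol, baseline to day 14). The comparison is to be "completed using an ANOVA for repeated measures and assessing the P value for time_x_group allocation". The next sentence is the significance rule: "P values <0.05 will be considered significant". It names no endpoint and no sidedness.

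Section 4.3 lists these secondary efficacy endpoints:

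- "Placebo-corrected percentage change in calculated LDL cholesterol from baseline to 72 hours": 1 comparison
- "Placebo-corrected percentage change in PCSK9 levels from baseline to 72 hours and 14 days": 2 comparisons
- "Placebo-corrected percentage change in Lp(a) levels from baseline to 72 hours and 14 days": 2 comparisons
- "Placebo-corrected percentage change in inflammatory markers (hsCRP, IL-6, IL-10, and TNF- α) from baseline to 72 hours and 14 days": 4 markers × 2 times = 8 comparisons

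That makes 1 + 2 + 2 + 8 = 13 listed comparisons. No secondary test is named, and no section gives an order, a multiplicity adjustment or an exploratory label.

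The inflammatory markers are not incidental. The objective in Section 2 is to determine the "effectiveness of alirocumab in further lowering cholesterol LDL and inflammatory biomarkers", and Section 10.4 includes a possible reduction of the inflammatory response in the hypothesis under test. Section 13.1 gives a power of 65–85% for CRP or IL-6 at 72 hours or 14 days, without choosing a marker or a time. It gives no power for IL-10 or TNF-α.

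**The concern.** Read as written, the rule lets any secondary P value below 0.05 be declared significant on the same footing as the primary result. For the inflammatory markers there are eight opportunities, none designated as the one that tests the objective. In a 20-patient trial, a single chance result on one marker at one time could then be reported as a significant effect on inflammation. It would answer half of the stated objective, and nothing in the plan would tell the reader how many comparisons stood behind it.

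The null is plausible for this group. Section 3 says the effects of PCSK9 inhibitors on inflammation in acute infarction are unknown, and Section 4.2 only suspects that the response may be blunted. For PCSK9 and Lp(a), by contrast, Section 4.2 expects reductions, and Section 13.1 expects a large LDL effect at two weeks.

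**Working it through.** The documents state no family-wise error rate, so there is no figure of the plan's own to reproduce on this point.

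**Inputs.** The threshold is 0.05 (Section 13.2). There are 8 inflammatory comparisons (Section 4.3), or 4 if the primary method is carried over as one time-by-group P value per marker. All inflammatory nulls are taken as true. The tests are assumed two-sided. Correlations between the tests are not in the documents, so a range is assumed.

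**Step 1: any false significant result, independent tests.** The chance is 1 − 0.95^k.

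- k = 8: 1 − 0.95^8 = 1 − 0.6634 = 33.7%, with 8 × 0.05 = 0.40 false positives expected.
- k = 4: 1 − 0.95^4 = 1 − 0.8145 = 18.5%.

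**Step 2: the eight comparisons with a common pairwise correlation r.** With z = 1.96, Φ and φ the standard normal distribution function and density, and u the shared component, the chance is

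1 − ∫ [Φ((z − √r·u)/√(1−r)) − Φ((−z − √r·u)/√(1−r))]^8 φ(u) du.

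**Step 3: a false result in the favourable direction only.** Fixing one direction per marker, each two-sided 0.05 test leaves 0.025 in that tail. With independent tests the chance is 1 − 0.975^8 = 1 − 0.8167 = 18.3%. With correlation, the lower-tail term in Step 2 is dropped.

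| Assumed r | Any false significant result | False favourable result |
|---|---|---|
| 0 | 33.7% | 18.3% |
| 0.2 | 31.9% | 16.3% |
| 0.3 | 30.0% | 15.2% |
| 0.5 | 25.0% | 12.5% |

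**Step 4: sensitivity to the correlation structure.** A simulation of eight two-sample t tests, 10 patients per arm and 40,000 runs, used separate assumed correlations between markers and between times. The chance of any false positive was 31.8% (markers 0, times 0.5), 27.7% (0.5 and 0.5) and 17.7% (0.8 and 0.8). Even the last is more than three times the nominal 5%.

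**Step 5: all 13 listed comparisons.** 1 − 0.95^13 = 1 − 0.5133 = 48.7%. This requires no effect on LDL at 72 hours, PCSK9 or Lp(a) as well, so it is a bound and not an estimate for this trial.

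**The case against.** The strongest reply has four parts.

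- **Scope.** The 0.05 sentence directly follows the primary-endpoint test and could be meant for it alone. That is possible, but the secondary endpoints would then have neither a method nor a rule for interpretation. The same clarification is needed on either reading.
- **Number of tests.** The plan lists 13 comparisons but does not specify 13 tests. Carrying the primary method over gives four inflammatory P values and 18.5%. This stands, and is why the result is given as a range.
- **Direction.** The two-sided figures include apparent worsening, which could not support an objective of lowering the markers. This also stands. For a false claim of benefit, 12–18% is the relevant range.
- **Existing safeguards.** There is one primary endpoint at one time point, the others are labelled secondary, and the inflammatory hypothesis is worded cautiously. That protects the primary test, but it does not stop a secondary P value from being declared significant.

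A reader might go further and infer from the 48.7% that a false significant finding somewhere among the secondary endpoints is likely. The documents do not support that. The figure is below one half even at its maximum, and it assumes no effect on outcomes where the protocol expects one. Nor do the documents show that all eight inflammatory tests have low power: only CRP and IL-6 have a stated power, and low power would not raise the false-positive rate in any case.

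**Conclusion.** The point holds for the eight inflammatory comparisons. If none of the four markers is affected, the plan as written carries up to about a 34% chance of at least one false significant result. That falls to about 25–32% at assumed common correlations of 0.5–0.2, and is 18.5% for four independent per-marker tests. A false favourable result has a chance of about 12–18% for the eight comparisons, assuming two-sided tests. The correlations are assumptions, and so is the reading that the 0.05 rule reaches the secondary endpoints. The type I error of the primary endpoint is not affected. This is a cheap improvement to what may be concluded from the secondary results, not a defect in the main comparison.

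**What to change.** Replace the significance sentence in Section 13.2 with:

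> *The primary endpoint is tested at two-sided alpha 0.05. Secondary endpoints, including all inflammatory markers, are exploratory: they are reported as between-group estimates with 95% confidence intervals and nominal P values, and are not declared statistically significant.*

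The level has to be written out because the documents do not settle it: Section 13.1 plans power at alpha 0.01, Section 13.2 analyses at 0.05, and neither states sidedness. The two sections should be reconciled in the same edit.

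The cost is that a secondary P<0.05, including for PCSK9, Lp(a), CRP and IL-6, is reported as nominal only. No patients are added and no alpha is spent.

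A Bonferroni correction over the eight tests (0.05/8 = 0.00625) would cost more. Assume 10 per arm and two-sided 0.05, and pair the stated 65% power with the 33% reduction and the 85% with the 50% reduction. The implied SDs are then about 30–31% and 35–37%, and power at 0.00625 falls to about 31–35% and 54–60%. If the sponsor wants a formal inflammatory claim, naming one marker at one time in advance is the simpler route.

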Patient will have blood samples (approximately 30 mL) drawn at baseline after signing the informed consent form but before receiving the study injection. The panel of biomarkers will include a lipid panel (total cholesterol, LDL-C, HDL-C, triglyceride levels, and Lp[a]), PCSK9 levels, inflammatory biomarkers (including hsCRP, IL-6, IL-10, and TNF- α), complete blood count (CBC), and complete metabolic panel (CMP).

After 3 days, or at the time of patient discharge (whichever occurs first), blood samples (approximately 30 mL) will be drawn again to re-measure the biomarkers listed above, and the patient will be given an appointment for a visit 14±3 days from enrollment. At their follow up visit, patients will undergo a repeat history and physical exam, and blood samples (approximately 30 mL) will again be drawn to re-measure the biomarkers listed above. This will complete the participation of the subjects in the clinical trial. The patient's clinical care will then continue on a regular basis, according to standard of care.

Biomarkers will be measured by LabCorp (Cincinnati, OH). The tubes will be collected by trained personnel, and immediately inverted 8-10 times after being drawn. Samples are then processed, refrigerated and shipped within 24 hours. The results from LabCorp will be sent securely to the PIs and designated investigators by email and/or fax.

For the measurement of the PCSK9 levels, not available commercially, we will collect samples, process them, and store them in a freezer located our lab for single batch analysis by Regeneron Pharmaceuticals, Inc. and Sanofi U.S.

10) POTENTIAL BENEFITS AND RISKS

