- The sponsor shall be responsible for ensuring submission of required expedited and periodic reports to the appropriate Regulatory Authority (RA), the Ethics Committee and investigators of each country participating in the Investigator-Sponsored Study (ISS, based on applicable regulations).
- Any Periodic reports (e.g. Development Safety Update Report (DSUR)), submitted to Regulatory Authority must first be transmitted to Regeneron/Sanofi for review and comment
- The Sponsor must provide to Regeneron/Sanofi any New Safety Findings pertaining to safety of the Investigational product within one (1) business day (e.g. Data Safety Monitoring Board recommendations).

12) DISCONTINUATION OF STUDY PARTICIPATION AND WITHDRAWAL

Patients may withdraw from the study at any time. The patient can decide to forgo any study procedures that makes him/her uncomfortable or wish not to complete. The study doctor may however stop the participation of the patient in this study at any time for many reasons including (*but not limited to*) the study doctor thinks it is necessary for patient health or safety, the patient has not followed study instructions, or administrative reasons requiring withdrawal.

Loss to follow-up can occur due to patients' withdrawal or death. If patients are lost to follow up and their clinical condition cannot be established (alive vs dead, hospitalized vs not), they will be excluded from the initial analysis, and then reintroduced for sensitivity analysis considering all potential outcomes. A 10% attrition rate is a reasonable assumption.

13) STATISTICAL CONSIDERATIONS

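### Section 13.2 names neither the visits in the primary repeated-measures ANOVA nor the handling of incomplete patients; a classical three-visit model would discard usable day-14 LDL values

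*Combined protocol and SAP*

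**What the plan says.** Section 4.3 defines the primary endpoint as "Placebo-corrected percentage change in calculated LDL cholesterol from baseline to day 14". It lists the 72-hour LDL change separately, as a secondary endpoint.

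Section 13.2 says that the primary comparison will be "completed using an ANOVA for repeated measures and assessing the P value for time_x_group allocation", at a 0.05 threshold. On missing values it says only "Missing data will not be input", which I read as no imputation. It does not say which visits enter the model, whether incomplete patients are deleted, or whether a sphericity correction applies.

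On sampling, section 4.1 says "Biomarkers will be collected at baseline, 3 days, and 14 days after randomization", and section 4.2 describes the LDL outcome over the same three times. Section 9 fixes the middle draw: "After 3 days, or at the time of patient discharge (whichever occurs first), blood samples" are taken.

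Section 12 says "The patient can decide to forgo any study procedures that makes him/her uncomfortable or wish not to complete". Its only rule for incomplete patients covers those lost to follow-up whose clinical condition cannot be established. A patient who attends on day 14 is not in that group.

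**The concern.** A classical repeated-measures ANOVA needs a value at every visit in the model. If day 3 is one of those visits and nothing is imputed, a patient whose primary endpoint was fully observed drops out of the primary test because a secondary-visit sample is missing. With 10 patients per arm, each such loss matters.

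Two further problems follow from the three-visit reading. The time-by-group test has two numerator degrees of freedom and asks whether the arms differ in LDL course over all visits, whereas the endpoint is day 14. The uncorrected F test also assumes that all pairwise visit differences have equal variance. That is doubtful when two visits lie about three days apart and the third comes some eleven days later.

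Under any reading, the set of patients in the primary test could be settled after the data are seen.

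**Working it through.** **Inputs.** Difference 40 points, SD 25%, 20 patients in total (section 13.1); 1:1 allocation (section 7); 10% attrition (section 12); 25% loss to follow-up (section 13.1); threshold 0.05 (section 13.2), taken as two-sided. The documents give no day-3 missing rate and no between-visit correlations, so both are assumed below.

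**1. The plan's own power figure.** Section 13.1 claims power above 99% at alpha 0.01 with 20 patients, and above 95% after 25% loss. For two groups, λ = δ / (SD·√(1/n₁ + 1/n₂)) = 40 / (25·√(1/10 + 1/10)) = 40/11.18 = 3.58, with 18 degrees of freedom. Two-sided power at 0.01 is 74.8% (84.2% by normal approximation). After 25% loss (7.5 per arm) it is 55.1% (69.9%). The stated figures are not reproduced with 10 per arm. The normal approximation reaches them with 20 and 15 per arm (99.4% and 96.5%). That is a separate matter. At the 0.05 threshold of section 13.2, 10 per arm gives 92.2%, which is the reference here.

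**2. Cost of dropping patients without day 3.** After 10% attrition, 18 day-14 values remain (9 per arm): λ = 40 / (25·√(2/9)) = 40/11.79 = 3.39, 16 degrees of freedom, power 89.0%. Suppose each of these patients lacks day 3 with probability m, independently. The complete patients per arm are then Binomial(9, 1−m), and power is the average over those counts. With 15 values (25% loss) the arms are 8 and 7.

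| Day-14 values | m = 0 | 10% | 20% |
|---|---|---|---|
| 18 | 89.0% | 84.4% | 78.5% |
| 15 | 81.5% | 75.8% | 68.8% |

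For 18 values, m = 2% gives 88.2% and m = 5% gives 86.8%. An analysis that keeps every day-14 value stays in the m = 0 column.

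**3. The three-visit F test itself.** The table uses a t-test on the change, so the F test was also simulated: 20 patients, 4,000 runs, equal correlation 0.5 assumed, day-14 effect 40.

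| Assumed day-3 effect | Nobody missing day 3 | 20% missing, dropped |
|---|---|---|
| 0 | 95.6% | 87.4% |
| 20 | 86.9% | 78.0% |
| 40 | 95.0% | 88.1% |

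A baseline/day-14 analysis of all day-14 values stayed at about 92% throughout.

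The first column shows that the test is not specific to day 14, because power changes with the day-3 effect while the day-14 effect is fixed. The interaction signal is the spread of the group differences (0, e₃, 40) around their mean:
- e₃ = 20: 20² + 0² + 20² = 800.
- e₃ = 0: 13.33² + 13.33² + 26.67² = 1,067.
- e₃ = 40: 26.67² + 13.33² + 13.33² = 1,067.

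**4. Type I error without a sphericity correction.** With equal variances σ², the variance of a visit difference is 2σ²(1−ρ). If ρ is 0.9 between baseline and day 3 and 0.4 with day 14, the variances are 0.2σ² and 1.2σ², a sixfold ratio. Null simulations with 10 per arm, correlations 0.8–0.9 between baseline and day 3 and 0.4–0.6 with day 14, rejected about 5.6% to 7.3% of the time. Under equal correlations the rate was about 5%. A Greenhouse-Geisser correction brought the patterns examined to 5.5% or less.

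**5. The two-visit reading.** With baseline and day 14 only, the time-by-group F is the square of the t-test on change. Day 3 plays no part, sphericity does not arise, and power is 92.2% (20 values) or 89.0% (18 values).

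**6. What ANCOVA adds.** With equal variances and ρ = 0.5, the SD of change is s·√(2·(1−0.5)) = s, so s = 25. The ANCOVA residual SD is 25·√(1−0.5²) = 21.7. In simulations with nobody missing, day-14 ANCOVA had about 96–97% power, against 88–96% for the three-visit F test, depending on the assumed correlations and day-3 effect.

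**The case against.** The strongest reply is that the plan never says that day 3 is in the primary model. Section 13.2 speaks of the interval change for the primary endpoint, section 4.3 defines that endpoint by baseline and day 14 alone, and 72-hour LDL is a separate secondary endpoint. A two-visit ANOVA is a fair reading, and under it no day-14 value is lost. This stands, and it makes the point conditional. It does not remove it, because sections 4.1, 4.2 and 9 make three visits at least as natural a reading.

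Listwise deletion is not stated either, and a no-imputation rule does not force it: a likelihood-based mixed model imputes nothing and keeps partial data. This also stands. But the plan names an ANOVA, and complete patients only is how the classical form works.

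A reader might infer that early discharge produces missing day-3 samples. Section 9 does not support that: the sample is taken at discharge if that comes first. Refused draws and lost samples remain. The right to forgo procedures in section 12 is general and shows no rate.

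The losses also depend on assumed rates. With 18 values, 2% to 5% missing costs only about 1 to 2 points of power, and the t-test figures are not exactly those of the F test. Both are fair limits on the size. The type I error figures likewise depend on the correlations chosen.

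**Conclusion.** The point holds as a conditional one. What is certain is that section 13.2 leaves open which visits and which patients make up the primary test.

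If a classical three-visit ANOVA is meant, usable day-14 values are discarded. Starting from 18 day-14 values, power falls from 89.0% to 86.8%, 84.4% or 78.5% for assumed day-3 missing rates of 5%, 10% or 20% (t-test approximation, two-sided 0.05). The test then also mixes day-3 and day-14 effects and, uncorrected, may reject about 5.6% to 7.3% of the time under the assumed correlations.

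Two stronger statements are tempting. One is that the plan drops every patient without a day-3 sample; the documents do not say so, and under a two-visit ANOVA it is untrue. The other is that the primary test exceeds its nominal 5%; no correlation is given in the documents, and a correction is neither specified nor excluded. The change is worth making anyway, because it fixes the analysis set in advance and gives a better-targeted test at no cost in data.

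**What to change.** State in section 13.2 that the primary test is the between-group contrast in LDL change at day 14, from an ANCOVA adjusted for baseline LDL. State that it uses every randomised patient with baseline and day-14 LDL, whether or not a day-3 sample exists. A mixed model for repeated measures with unstructured covariance, testing the day-14 contrast, is an acceptable alternative; Kenward-Roger degrees of freedom suit a trial of this size. If the sponsor prefers to keep the ANOVA, naming baseline and day 14 as its only visits removes the loss of patients and the sphericity problem, but forgoes the gain from baseline adjustment.

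None of these imputes data, so the existing sentence on missing data can stand. The cost is one sentence, with no extra patients, samples or visits. It should be in place before unblinding.
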